#### **4.1.1 Analysis time points**

##### **4.1.1.1 Study periods**

The study periods are as follows:

- Screening Period (Visit 1: Day -28 to -1)
- Sampling Period (Visits 2 to 8: Days 1 to 7)
- SFU Period (Days 8 to 57)

A study participant is considered to have completed the study if she has completed all periods of the study including the SFU period and did not discontinue the study early.

Visit 9 is a SFU telephone call which will occur on Day 57 ( $\pm 5$  days).

#### 4.1.1.2 Visit variables

The visit variables will be reported in the TFLs as per [Table 4-1](#).

**Table 4-1: Visit variables**

Visit name in the protocol	Visit variable to be displayed in TFLs
V1 (Week -4 to -1, Day -28 to -1)	Screening
V2 (Week 1, Day 1)	Day 1
V3 (Week 1, Day 2)	Day 2
V4 (Week 1, Day 3)	Day 3
V5 (Week 1, Day 4)	Day 4
V6 (Week 1, Day 5)	Day 5
V7 (Week 1, Day 6)	Day 6
V8 (Week 1, Day 7)	Day 7
EW (Week 1, Day 7)	Early Withdrawal
SFU (Week 9, Day 57)	Day 57 (SFU)

EW=early withdrawal, SFU=safety follow-up, V=visit.

Note: Early Withdrawal should only be used for participants who terminate the study early.

#### 4.1.1.3 Relative day for listings

Relative day for an event or measurement occurring before the date of the first dose will be calculated as follows:

$$\text{Relative Day} = \text{Event/Measurement Date} - \text{Date of First Dose}$$

Relative day for an event or measurement occurring on the date of the first dose is 1.

Relative day for an event or measurement occurring on the date of the first dose will be calculated as follows:

$$\text{Relative Day} = (\text{Event/Measurement Date} - \text{Date of First Dose}) + 1$$

Relative day for an event or measurement occurring after the date of the first dose to the date of the last visit will be calculated as follows:

$$\text{Relative Day} = +(\text{Event/Measurement Date} - \text{Date of First Dose})$$

There is no relative day 0. Relative day will not be calculated for partial dates, instead relative day will be presented as '--' in the relevant participant data listing.

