- f Study participant's eligibility will be rechecked. Results of clinical laboratory tests (hematology, clinical chemistry, urinalysis) from the Screening Visit may be used at the investigator's discretion.
- g Changes in medical history since the Screening Visit will be collected.
- h Height will be measured at Screening only. Weight will be measured with the study participant wearing no shoes and light clothing at Screening and predose on Day 1.
- i A complete physical examination will be performed predose on Day 1. A complete physical examination includes, at a minimum, general appearance; ear, nose, and throat; eyes, hair, and skin; and assessments of the cardiovascular, respiratory, gastrointestinal, neurological, musculoskeletal, and hepatic systems, breasts, nipples (for signs of mastitis or nipple cracks), and, if relevant, post-Cesarean scar (for signs of infection or abscess).
- j Vital signs comprise systolic and diastolic blood pressure, pulse rate, respiratory rate, and body temperature, and should be measured in a semi-supine position after 5 minutes rest. On Day 1, vital signs will be measured predose and at approximately 15 minutes and 3 hours after the end of the infusion. On Days 2, 3, 4, 5, 6, and 7, vital signs will be measured once per day. Vital signs should be measured/taken before blood sampling, where applicable. Study participants will be monitored for clinical signs and symptoms of hypersensitivity reactions during rozanolixizumab administration.
- k All ECG recordings should be taken with the study participant resting in the supine position for at least 5 minutes.
- l Serum pregnancy test at Screening and urine pregnancy test on Day 1 and on Day 7.
- m See Appendix 2 (Section 10.2) for the list of clinical laboratory tests to be performed. Laboratory tests with values considered clinically significantly abnormal should be repeated as described in Section 8.2.5.
- n Clinical laboratory tests (hematology, clinical chemistry, and urinalysis) will be performed predose on Day 1.
- o The blood sampling time points will be: predose (within 60min before dosing) and 6h ( $\pm 6$ min), 9h ( $\pm 6$ min), 12h ( $\pm 12$ min), 24h ( $\pm 30$ min) (Day 2), 48h ( $\pm 30$ min) (Day 3), 72h ( $\pm 30$ min) (Day 4), 96h ( $\pm 30$ min) (Day 5), and 144h ( $\pm 24$ h) (Day 7) after the start of infusion.

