#### 4.1.2 Definition of baseline values

Baseline for vital signs, hematology, clinical chemistry, or urinalysis measurements is defined as the last available measurement (scheduled or unscheduled) prior to dosing.

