#### 4.5.2 Clinical laboratory evaluations

Treatment-emergent marked abnormalities (TEMA) in laboratory parameters may be analyzed. Thresholds for defining marked abnormalities for relevant laboratory parameters are available in [Appendix 6.11.1](#). MA values are considered treatment-emergent if the MA was not present before the date of first administration of the study drug and occurred on or after the date of the first administration of the study drug and before the end of the study.

Measurements below the lower limit of quantification (BLQ) will be imputed with half of the lower limit of quantification (LLOQ), and measurements above the upper limit of quantification (ALQ) will be imputed to the upper quantification limit for purposes of quantitative summaries.

Listings of clinical chemistry and hematology laboratory results will be produced for participants who had a value outside the normal ranges, including any values which are clinically significant as assessed by the investigator. These listings will include all data for each parameter for which a participant has at least one abnormal value during the study. Laboratory variables will be grouped according to the laboratory function panel (e.g., lipids, endocrine) and will be categorized as normal, high or low, if applicable, based on the reference range supplied by the analytical laboratory.

Clinical chemistry and hematology parameters will be summarized by visit for both absolute values and changes from Baseline.

Liver function laboratory results will be listed for study participants with elevated liver function results.

Urinalysis laboratory results will be listed but not summarized.

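### Two SAP date rules are wrong as written: relative day after dosing omits the +1, and a marked laboratory abnormality first seen in the Day 1 predose sample qualifies as treatment-emergent

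*SAP*

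**What the plan says.** **Relative day.** SAP 4.1.1.3 fixes the dosing date: "Relative day for an event or measurement occurring on the date of the first dose is 1". It then gives a formula with +1, but confines it to that same date. The third case, "Relative day for an event or measurement occurring after the date of the first dose to the date of the last visit", takes the event date minus the first-dose date, with a leading plus sign and no 1 added. The section also states: "There is no relative day 0". SAP Table 4-1 labels the day after dosing Day 2, the last sampling visit Day 7 and the safety follow-up (SFU) call Day 57.

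**Laboratory data.** SAP 4.5.2 says that treatment-emergent marked abnormalities may be analyzed. To qualify, an abnormality must be absent before the date of first administration and must have "occurred on or after the date of the first administration of the study drug and before the end of the study". The footnote to Table 1-1 of the protocol says: "Clinical laboratory tests (hematology, clinical chemistry, and urinalysis) will be performed predose on Day 1". SAP 4.1.2 says that Baseline for laboratory values "is defined as the last available measurement (scheduled or unscheduled) prior to dosing". By contrast, the TEAE definition in SAP 4.3.1.1 works from the start date and time relative to dosing.

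**The concern.** Numbering without a day 0 needs +1 on every date from dosing onward. Here the +1 is attached only to the dosing date, where it merely restates the value 1. A programmer who follows the text gives two calendar dates the same number, and the relative-day column then disagrees with the visit labels in the same outputs.

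The laboratory rule looks only at the calendar date, while the scheduled sample on that date is taken before the drug is given. The same value can therefore be a participant's Baseline and also be counted as having emerged on treatment.

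Safety is the secondary objective. With 12 to 15 participants planned to provide data, individual listings carry much of the safety review, and a single wrong flag is visible in a percentage.

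**Working it through.** **1. Relative day**

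Inputs: dosing date d0 has relative day 1, and a later date d has relative day d − d0 (SAP 4.1.1.3). Labels come from SAP Table 4-1 and the study periods in SAP 4.1.1.1.

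The SAP's own convention first: the SFU call is 8 weeks after dosing, and 8 × 7 = 56 days. SAP 1.2 calls this Day 57, which is 56 + 1. The visit labels therefore use (d − d0) + 1.

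| Days after dosing | Label | SAP 4.1.1.3 | (d − d0) + 1 |
|---|---|---|---|
| 0 | Day 1 | 1 | 1 |
| 1 | Day 2 | 1 | 2 |
| 2 | Day 3 | 2 | 3 |
| 3 | Day 4 | 3 | 4 |
| 4 | Day 5 | 4 | 5 |
| 5 | Day 6 | 5 | 6 |
| 6 | Day 7 | 6 | 7 |
| 7 | Day 8, start of SFU Period | 7 | 8 |
| 56 | Day 57 | 56 | 57 |

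Value 1 covers two dates. Each later date is one too low. The first day of the SFU Period gets 7, which SAP 4.1.1.1 places in the Sampling Period (Days 1 to 7). Applying +1 throughout reproduces every label. Negative days are unaffected.

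**2. Treatment-emergent marked abnormality**

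Inputs: scheduled laboratory samples are at Screening, V2 and V4 (protocol Table 1-1), which are Screening, Day 1 and Day 3 in SAP Table 4-1. Day 1 is predose. Each sample either shows the marked abnormality or does not, giving 2 × 2 × 2 = 8 patterns.

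- SAP rule: absent at Screening, and present on Day 1 or Day 3.
- Dosing date/time rule: absent at Screening and on Day 1 predose, and present on Day 3.

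| Screening | Day 1 predose | Day 3 | SAP rule | Date/time rule |
|---|---|---|---|---|
| absent | absent | absent | no | no |
| absent | absent | present | yes | yes |
| absent | present | absent | **yes** | no |
| absent | present | present | **yes** | no |

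The four patterns with the abnormality already present at Screening are flagged by neither rule. The SAP rule thus flags 3 of the 8 patterns and the date/time rule flags 1. The two that differ are those in which the abnormality is first seen before dosing on Day 1. Neither is a new finding against Baseline when Baseline is that Day 1 sample.

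Bilirubin is an exception. SAP Table 6-4 sets its limit at more than 3 × ULN if Baseline is normal, and more than 3 × Baseline otherwise. If the Day 1 predose value is itself Baseline, a normal value cannot exceed 3 × ULN, and an abnormal one cannot exceed three times itself.

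A new Day 1 abnormality need not prevent dosing: the Table 1-1 footnote on rechecking eligibility lets the investigator rely on the Screening laboratory results.

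**The case against.** **The leading plus sign.** It may be meant as a display prefix, so that +1 denotes one day after dosing and is distinct from 1. That is possible, but the SAP does not say so, and the numbers would still be one below the visit labels.

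**Reach of relative day.** The section concerns listings only. Visit labels come from Table 4-1, and relative day is not calculated for partial dates. No summary or endpoint is shown to use it. This stands and limits the effect.

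**Rarity of the laboratory case.** The summary is optional. It covers marked abnormalities only, mostly CTCAE Grade 3 or higher, in healthy women screened for liver enzymes, neutrophils and lymphocytes. The abnormality must also have been absent from all samples before the dosing date. This stands too: the error is in the rule and may never appear in the data.

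**Stronger readings that the documents do not support:**

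- *The anaphylaxis rule is damaged.* SAP Table 6-1 accepts onset on the injection day or one day after, and is worded on dates. Both days qualify, so the duplicated number changes nothing.
- *Dosing-day and next-day adverse events cannot be told apart.* SAP 4.3.1.2 lists onset date and time for every event, which separates them.
- *Predose findings would be attributed to the drug.* The flag is a temporal label, not a causality assessment. SAP 4.5.2 also provides changes from Baseline, and its chemistry and hematology listings give all data for any parameter with an abnormal value.

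**Conclusion.** Both rules give a wrong output when followed literally.

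- **Relative day:** off by one for every complete date after dosing up to the last visit, with the value 1 used twice. This rests on the visit labels being the intended numbering, which SAP 1.2 and Table 4-1 support.
- **Laboratory rule:** 2 of 8 patterns are misclassified, if the optional analysis is done, and not for bilirubin when the Day 1 predose value is Baseline. The documents give no basis for estimating how often this would occur. If it happened once, and the denominator were the planned 12 to 15 participants, the false flag would be 1/15 = 6.7% to 1/12 = 8.3% of participants.

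The consequences are confined to safety listings and that laboratory summary. TEAE classification uses date and time, and PK parameters use actual sampling times, so neither is affected. These are small corrections, best made before programming.

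**What to change.** 1. **SAP 4.1.1.3:** use (date − first-dose date) + 1 for all dates on or after dosing, and delete the separate rule for later dates. Keep the rule for dates before dosing.
2. **SAP 4.5.2:** define a marked abnormality as treatment-emergent if it is absent from every sample before the dosing date and time, including Day 1 predose, and present in a sample after it. An abnormality seen at Screening, gone on Day 1 and back on Day 3 then stays non-emergent, as it is now.

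The cost is two sentences in the SAP. No data collection, analysis set or endpoint changes.

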#### 4.1.1.4 Handling of repeated and unscheduled measurements

All repeated and unscheduled measurements will be presented in the listings, where applicable. The following general rules will apply to all repeated and unscheduled measurements, unless otherwise specified:

- For repeated or unscheduled measurements obtained prior to the first dose of IMP the latest non-missing value (scheduled or unscheduled) will be used in the calculation of descriptive statistics (i.e. Baseline);
- For repeated or unscheduled measurements obtained at any time point after the first dose of IMP, the scheduled values (if non-missing) will always be used in the calculation of changes from Baseline and for the descriptive statistics (i.e., in summaries by time point). If repeated scheduled values are obtained at any time point, the latest non-missing values will be used.

#### 4.1.2 Definition of baseline values

Baseline for vital signs, hematology, clinical chemistry, or urinalysis measurements is defined as the last available measurement (scheduled or unscheduled) prior to dosing.

#### 4.1.3 Date Imputation

Partial dates/times may be imputed for the following purposes:

- Classification of adverse events (AEs) as treatment emergent
- Calculation of AE durations
- Classification of medications as past, prior, or concomitant

Imputed dates will not be shown in the listings; all dates will be displayed as reported in the database. Any partial dates should be queried and resolved prior to database lock (DBL).

The following rules will be applied for partially or completely missing start dates and times:

- If the **day** is missing, and the year and month are:
  - the same as the month-year of the first dose of IMP then assign the day of first dose of IMP. If the imputed start date is after the specified end date, then assign the day of screening date. If this results in the imputed start date is after the specified end date, then assign the first of the month;
  - not the same as the month-year of the first dose of IMP then assign the first of the month.
- If **month and day are missing**, and year is:
  - the same as the year of the first dose of IMP then assign the month-day of first dose of IMP. If the imputed start date is after the specified end date, then assign the month-day of screening date. If this results in the imputed start date is after the specified end date, then assign January 01;

- not the same as the year of the first dose of IMP then assign January 01.
- If **year, month and day are all missing** then assign the date of first dose of IMP. If an imputed start date is after the specified end date, then assign January 01 of the year of the end date, or the date of screening if this is later (if the latter imputation results in an end date that is earlier than the start date, then use January 01).
- If the **time** is missing, then assign time of first dose of IMP, if not missing. Otherwise, impute start time as 00:00h.

The following rules will be applied for partially or completely missing end dates and times:

- If the **day** is missing, then use the last day of the month. If an imputed stop date is after last contact date and last contact date is before the data cut-off date, then assign last contact date as the stop date. If an imputed stop date is after last contact date and last contact date is after the data cutoff date, then assign data cutoff date as the stop date.
- If **month and day** are missing, then use December 31 of the known year. If an imputed stop date is after last contact date and last contact date is before the data cutoff date, then assign last contact date as the stop date. If an imputed stop date is after last contact date and last contact date is after the data cutoff date, then assign data cut-off date as the stop date.
- If **year, month and day** are all missing, then use discharge date or data cut-off date.

Discharge date refers to the date of the end of study visit for completed participants or the date of discontinuation for participants that were withdrawn. For any AEs with known start date after the date of discontinuation, the date of last contact will be used as the discharge date. For participants still ongoing in the study at the time of the data cut-off, and for whom no discharge date is available, the date of the data cut-off will be used instead of the discharge date.

- If the **time** is missing, then set to 23:59h.

Any medication with a start date on the first dosing date will be assumed to be concomitant.

Any level of imputed AE dates and times will be used for the calculation of duration of AEs as described in Table 4-2. Duration will be displayed in listings as days, hours and minutes.

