**Table 4–2: Calculation rules for duration of adverse events**

Data availability	Calculation rules
Complete start and end date/times	Duration = end datetime – start datetime
Start date or time imputed	Duration <= end datetime – start datetime
End date or time imputed	For ongoing AEs: 

● Duration >= end datetime – start datetime

 For resolved AEs: 

● Duration <= end datetime – start datetime

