### **4.3 Secondary endpoints analysis**

#### **4.3.1 Treatment-emergent adverse events**

##### **4.3.1.1 Definition of endpoint**

All adverse events (AEs) will be coded using MedDRA® version 27.1 and characterized as pretreatment and treatment emergent according to the intake of treatment. Adverse events with a start date prior to the first and only dose of treatment will be defined as pretreatment AEs. A TEAE is defined as any AE with a start date/time on or after the dosing of study medication until 8 weeks (56 days) inclusive after dosing of study medication.

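### The SAP's rule for a missing AE start time ignores the recorded end, so a Day 1 event that was over before dosing can be counted as treatment-emergent

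*SAP*

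**What the plan says.** SAP 4.1.3 allows partial dates and times to be imputed for stated purposes. The first is "Classification of adverse events (AEs) as treatment emergent"; the next is the calculation of AE durations. For a missing start time the instruction is: "then assign time of first dose of IMP, if not missing. Otherwise, impute start time as 00:00h". It is not restricted to the dosing date.

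The rules for missing start dates do look at the end of the event. The missing-day rule, for example, continues: "If the imputed start date is after the specified end date, then assign the day of screening date". The missing-month and fully missing rules have similar fallbacks. All of them compare dates, and the time rule has no counterpart.

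SAP 4.3.1.1 then classifies events: "A TEAE is defined as any AE with a start date/time on or after the dosing of study medication", up to 56 days inclusive. The companion definition is: "Adverse events with a start date prior to the first and only dose of treatment will be defined as pretreatment AEs".

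On duration, SAP 4.1.3 says: "Any level of imputed AE dates and times will be used for the calculation of duration of AEs". In Table 4-2, the row "Start date or time imputed" prints "Duration <= end datetime – start datetime". SAP 4.3.1.2 lists onset and outcome date and time for each event, with derived duration and derived time to onset.

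**The concern.** TEAE occurrence is the secondary safety endpoint. AEs are collected from consent (Protocol 8.3.1), participants may be admitted early on Day 1 or the evening before, and predose blood sampling and breast pumping take place before the infusion. A short event can therefore begin and end on Day 1 before exposure. If its start time was not captured but its end time was, the data already show that it is not treatment-emergent, yet the rule makes it so.

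The listings have a separate problem. The clock time of the dose says nothing about when an event began on any other day. Using it there can place the start after the recorded end, or turn a stated upper bound on duration into a figure below the true duration. Imputed dates are not displayed in the listings, so a reader could not easily trace an odd duration to its cause.

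**Working it through.** The SAP gives no figure to reproduce, so the check applies the written rules to test events.

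**Inputs.** The start-time rule, date fallbacks and use in durations come from SAP 4.1.3. The TEAE and pretreatment definitions come from SAP 4.3.1.1, and the duration bounds from Table 4-2. The planned 12 to 15 participants come from SAP 1.2. The dose clock time is not in the documents; 09:00 is assumed, with a range of 08:00 to 12:00.

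**Rule.** Imputed start = start date (reported or imputed) + dose clock time. Printed duration = recorded end minus imputed start, shown as `<=`.

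| Test event | Imputed start | Class under SAP | Printed duration, dose 09:00 | Dose 08:00 to 12:00 |
|---|---|---|---|---|
| A. Day 1, no start time, ended 1 h before dose | Day 1 09:00 | TEAE (wrong) | 8 - 9 = -1 h | -1 h throughout |
| B. Day 3, no start time, ended 07:00 | Day 3 09:00 | TEAE (correct) | 7 - 9 = -2 h | -1 h to -5 h |
| C. Day 3, no start time, truly 02:00 to 20:00 (18 h) | Day 3 09:00 | TEAE (correct) | 20 - 9 = 11 h | 12 h to 8 h |
| D. Start date and time missing, ended Day 1, 1 h before dose | Day 1 09:00 | TEAE (wrong) | 8 - 9 = -1 h | -1 h throughout |

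- **A:** an imputed start equal to the dose meets the TEAE definition. The pretreatment definition is worded by start date and does not clearly rescue an event dated Day 1.
- **B:** classification is right and duration is impossible.
- **C:** the printed bound is 18 - 11 = 7 h too short. A `<=` is guaranteed only if the imputed start is the earliest possible one.
- **D:** the date fallback does not trigger, because imputed start and end share a date. The time rule then puts the start after the end.

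**Size for the endpoint.** One participant is 1/12 = 8.3 percentage points or 1/15 = 6.7 points.

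**Rerun with the rule under the fix.** A becomes pretreatment, 8 - 0 = at most 8 h (7 to 11 h over the range). B stays a TEAE, at most 7 h. C stays a TEAE, at most 20 h, which contains the true 18 h. D becomes pretreatment with a positive 8 h (7 to 11 h). Because D's start date is itself imputed, its 8 h is not a guaranteed maximum, so Table 4-2 needs attention too.

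**The case against.** The strongest reply is that the endpoint is exposed in only one narrow case: the start date is Day 1 (reported or imputed), the start time is missing, the end time is recorded, and that end precedes dosing. The participant is then in the clinic with staff, event times are planned data, and with 12 to 15 women a record that ends before it begins would be conspicuous. SAP 4.1.3 also asks for partial dates to be queried before lock. Counting a Day 1 event of truly unknown timing as a TEAE is ordinary conservatism. All of this stands, and it limits the point. It does not remove it: the query sentence names dates, not times; the rule exists for values that stay unresolved; and conservatism does not extend to an event whose recorded end proves it was over.

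A reader might infer that every AE with a missing start time is mishandled. That goes too far. If the dose time is missing, the rule gives 00:00h. For events dated after Day 1, clock time cannot change TEAE status. If the end time is missing as well, it becomes 23:59h: a true 06:00 to 08:00 event on Day 3 with a 09:00 dose is then shown as at most 14 h 59 min, a positive duration and a valid bound.

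A reader might also attach a frequency. With true start uniform over a non-dosing day and the end time recorded, the bound is false in 9/24 = 37.5% of such events (8/24 = 33% to 12/24 = 50%), and a 2-hour event gets a negative duration in (9 - 2)/24 = 29% (25% to 42%). These only restate the assumed dose hour. The documents give no dose time, no distribution of start times and no rate of missing times, so they are not estimates for this trial.

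**Conclusion.** The point holds as a minor one. As written, the start-time rule turns a Day 1 event with a recorded end before dosing into a TEAE, contrary to SAP 4.3.1.1. It also gives a negative listed duration to any event whose recorded end, on its start date, is earlier than the dose clock time. After Day 1 the damage is confined to listed duration and time to onset, including a `<=` that can be false when the end time is recorded; SAP 4.3.1.2 names no summary table of durations.

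The 8.3 and 6.7 points are maxima. SAP 4.3.1.2 counts each participant once, so any-TEAE incidence moves only if she has no other TEAE. The Safety Set includes everyone dosed, even partially, and withdrawals before Day 7 may be replaced (Protocol 7.2), so the denominator may exceed 15 and the shift be smaller. The frequency cannot be derived from the documents. The classification result needs no assumed dose time; the hours in the examples do. The PK endpoints are untouched, and no hypothesis is tested.

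**What to change.** Replace the start-time rule in SAP 4.1.3 with:

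> *If the start time is missing and the start date (reported or imputed) is the dosing date, assign the time of first dose, unless the recorded AE end date/time is before dosing; in that case assign 00:00h and classify the AE as pretreatment. On any other date assign 00:00h.*

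Keep 00:00h for a missing dose time. The explicit pretreatment instruction is needed because 4.3.1.1 defines pretreatment by start date, which does not clearly cover an event placed at 00:00h on Day 1.

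This wording alone does not make Table 4-2 correct. A Day 1 event that began before dosing and ended after it still gets a start that is too late, and the date rules can assign the dosing date when an earlier one is possible. So print `<=` only when the imputed start is the earliest possible start. For ongoing AEs with both start and end imputed, the table prints `>=`, which is not guaranteed under either start time; show duration there as not determinable.

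The cost is two sentences and a table edit in the SAP, one programming condition for the start time and the matching display rule for durations. No new data are needed.
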